## **6.12. EEG pre-processing**

### **6.12.1. EEG device and feedback specifications**

The neurofeedback device (NeuroConn THERA-PRAX) included a trainer screen and a client screen, and the neurofeedback apparatus (Item 4e of the CRED-nf checklist). Participants in the EEG group received the NF treatment using visual stimuli as reinforcement (Item 4c of the CRED-nf checklist). Specifically, two bar graphs depicting real-time beta band activity and muscular activity were presented (Item 4b of the CRED-nf checklist).

### **6.12.2. EEG pre-post recording**

Changes in EEG spectral power during 180s resting-state eyes-open, 180s eyes-closed, and during 90s of food picture presentation will be analysed based on EEG recordings before the first and before the last neurofeedback session. A band-pass filter and a notch filter will be used to filter EEG data. The continuous EEG will be segmented in 2 s intervals and ocular artefact correction will be applied. Further, automatic artefact rejection will be applied to segments with voltage steps greater than 50  $\mu\text{V}/\text{ms}$  and amplitudes exceeding  $\pm 100 \mu\text{V}$ . After these automated procedures, all data will be visually assessed by an extensively trained researcher in order to identify and remove residual contaminants (e.g., artefacts, focal abnormalities, drowsiness). Based on this assessment, at least 30 artefact-free segments (not necessarily consecutive) of the filtered EEG data will be required for the eyes-open and eyes-closed condition to be included in the analysis. The number of removed segments will be reported (Item 3e of the CRED-nf checklist). The filtered EEG data will then be Fourier transformed with a Hanning window length of 20% extracting theta ( $\theta$ , 3.5–7.5 Hz), alpha ( $\alpha$ , 7.5–12.5 Hz), and beta ( $\beta$ , 12.5–30 Hz) frequency bands. The extracted absolute power for each frequency band will be converted to

relative band power (%) and ln-transformed before statistical hypotheses testing to obtain normally distributed data.

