### 7.4.2 Statistical error terms

The level of significance is set at  $\alpha = 5\%$ , aiming for a power of  $1 - \beta = 80\%$ .

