## d) Brain-activity-related outcomes

- fNIRS and fNIRS delayed treatment group, group-wise: Condition-(neurofeedback/transfer), block(first block/second block) and task-wise (regulation/mirror/rest) oxygenated, deoxygenated, and total haemoglobin values per session for the 2 individual fNIRS channels that were selected for training and for regions of interest.
- EEG group only (T0, T1): Eyes-closed (3min) and eyes-open (3min) resting-state and food-specific activity (90s) for theta, alpha, and beta band in  $\mu\text{V}$
- EEG group only: mean beta activity baseline and feedback in  $\mu\text{V}$  per session noted from TheraPrax device, amount of successful trials and % success in transfer trial per session

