### **4.4.2 Within-session and between-session comparisons (CRED-nf 5b/5c)**

Mean beta band activity in  $\mu\text{V}$  for baseline, feedback and transfer trial will be displayed graphically per session.

For within-session variability, two mixed effects models (one for feedback and one for transfer) will be used. The dependent variable is the mean power in the  $\beta$  band and the fixed effects are the (constant) baseline mean power in the  $\beta$  band and the number of the trial, treated as a numerical variable (i.e. assuming linear behaviour over time). The patient is the random term.

To assess the success of the feedback relative  $\beta$  band power will be shown graphically for resting state eyes open, eyes closed, and food cue presentation at pre and post treatment. Paired t-test of the logarithms of these values will be used for formal testing with Bonferroni-Holm correction for the three states.

For comparison with a “control” condition, the difference of  $\beta$  band power on a logarithmic scale (i.e. logarithm of the ratio) from feedback to its baseline will be compared to the difference from transfer to its baseline. These differences will be treated in a mixed model with condition (feedback vs transfer) and session number fixed effects along with their interaction and patient as a random variable. The interaction term will quantify a potential learning effect, i.e. that the feedback in the later sessions is no longer necessary and the difference between the conditions gets smaller.

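### EEG segments are removed by eye, with no masking to pre or post, before a single-arm paired test of ln relative beta power

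*SAP*

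**What the plan says.** SAP 6.12.2 compares "EEG recordings before the first and before the last neurofeedback session" in three states: eyes open and eyes closed (180 s each) and food pictures (90 s). Data are cut into 2 s segments, corrected for ocular artefacts, and passed through fixed thresholds: "automatic artefact rejection will be applied to segments with voltage steps greater than 50" µV/ms or beyond ±100 µV. After that, "all data will be visually assessed by an extensively trained researcher in order to identify and remove residual contaminants", with artefacts, focal abnormalities and drowsiness as the examples. At least 30 clean segments are required in each resting state; no minimum is given for food pictures. The number of removed segments is to be reported under CRED-nf Item 3e. Band power is then made relative and ln-transformed.

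SAP 2.2(d) restricts these recordings to one arm: "EEG group only (T0, T1): Eyes-closed (3min) and eyes-open (3min) resting-state". SAP 4.4.2 gives the purpose, "To assess the success of the feedback relative" beta power is plotted at pre and post, and the test: "Paired t-test of the logarithms of these values will be used for formal testing with Bonferroni-Holm correction for the three states".

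On blinding, Protocol 3.2 has assessors blind to study hypotheses and randomization. The CRED-nf table in the SAP answers Item 2c (blinding of outcome raters) by pointing to the protocol. Neither text mentions the EEG review or the visit. SAP section 4 calls the neurophysiological analyses explorative.

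**The concern.** The visual step is a judgement about which data count. A reviewer who knows that a file is a post-treatment file, or who reads all pre files before all post files, may apply a different standard at the two visits. In a two-arm comparison much of such a difference would cancel. Here only one arm has the recordings, so nothing offsets it. Blinding to randomization does not help either, because every file comes from the same arm.

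The contrast is the one the SAP uses to judge whether feedback worked on these recordings. A difference in cleaning could produce an apparent change in relative beta, or hide a real one.

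**Working it through.** **No figure to reproduce.** The SAP states no sample size, SD or power for this test. The check has three parts: the room for judgement, the effect of an assumed shift on the test, and whether Holm protects.

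**1. Room for judgement (SAP 6.12.2, non-overlapping segments assumed).**
- Resting states: 180 / 2 = 90 segments, of which 30 must survive. Up to (90 − 30) / 90 = 67% can be removed, by all steps together, and the recording is still analysed.
- Food pictures: 90 / 2 = 45 segments, with no stated minimum.

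**2. Effect of a shift on one paired t-test.** Inputs:
- α = 5% (Protocol 7.4.2). Two-sided is assumed, because sidedness is not stated for this test.
- n = 26 randomized per arm (Protocol synopsis), or 21 per arm analysed (Protocol 7.4.4: 42 in two pooled arms). The actual EEG data set size is not given.
- b = the shift in mean ln relative beta caused by cleaning, in SDs of the paired difference. This is an assumption; nothing in the documents fixes it.

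With no true change, the test statistic is noncentral t with n − 1 degrees of freedom and noncentrality b√n. For b = 0.2 this is 0.2 × √21 = 0.92 or 0.2 × √26 = 1.02, against two-sided critical values of 2.086 and 2.060.

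| b (SD) | n = 21 | n = 26 |
|---|---|---|
| 0 | 5.0% | 5.0% |
| 0.1 | 7.2% | 7.8% |
| 0.2 | 14.1% | 16.5% |
| 0.3 | 25.8% | 31.3% |

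These rates count rejections in both directions.

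**3. Holm.** Holm compares the smallest of the three p-values with 0.05 / 3. It corrects for the number of tests, not for a displaced mean. By simulation (40,000 runs, correlation between states 0 or 0.5), a shift of 0.2 SD in all three states gives at least one rejection in 15–17% (n = 21) or 18–21% (n = 26). With no shift the figure is 4.4–5.0%.

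**4. What a leakage difference means on the tested scale.** The SAP tests relative, not absolute, beta. Assume that a missed contaminated segment doubles beta only, that beta is 30% of total power, and that 10% of segments are contaminated and missed at pre against 5% at post.
- Pre: 0.30 × 1.10 / (0.70 + 0.30 × 1.10) = 0.3204.
- Post: 0.30 × 1.05 / (0.70 + 0.30 × 1.05) = 0.3103.
- Shift: ln(0.3103 / 0.3204) = −0.032. On absolute beta it would be ln(1.05 / 1.10) = −0.047.
- With an assumed SD of the paired difference of 0.25, b = 0.032 / 0.25 = 0.13, and the rejection rate is about 9% (n = 21) to 10% (n = 26).

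If contamination doubled power in all bands, relative beta would not move. The result depends on the contamination model, so the table in SD units is the safer summary.

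**The case against.** Several points on the other side stand.

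- The SAP is silent on masking; it does not say that review was or will be unmasked. A reader might infer that cleaning was in fact unblinded, or that rater drift has distorted the result. The documents support neither. Drift biases the contrast only if reading order follows visit, and no order is stated. Removal unrelated to relative beta adds noise, not bias. Expectation from knowing the visit, however, needs no particular order.
- The visual step follows ocular correction and fixed thresholds. Removals are already to be reported under Item 3e, which asks for condition and group effects for artefacts. A split by visit is not specified.
- A reader might take this as the one test of whether EEG training changed brain activity. It is not. SAP 4.4.1 and 4.4.2 also plan per-session success rates, two within-session mixed models and a feedback-versus-transfer model. SAP 6.12.3 bases the session-wise data on device output, with no cleaning by eye described, and the brain–behaviour model in 4.4.3 uses the proportion of successful trials.
- A reader might quote a false-positive rate computed from absolute beta. That is the wrong variable: the conversion to relative power shrinks such a shift or removes it.
- Masking does not make an uncontrolled pre-post change attributable to feedback.

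These points limit the weight of the concern. They do not close the route: no stated safeguard keeps the visit from the reviewer.

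**Conclusion.** The point holds, for one exploratory test. The plan lets a judgement-based removal step, not masked to visit in the text, feed a single-arm paired contrast. Any visit-related difference in cleaning that is related to relative beta passes into the estimate. How large it would be, and in which direction, cannot be taken from the documents. Under an assumed shift of 0.1 to 0.3 SD of the paired difference, the nominal 5% becomes about 7–8% at the low end and 26–31% at the high end (two-sided, n = 21 to 26), and Holm does not bring it back. The primary OBE analysis, the comparisons between arms and the session-wise device measures are untouched. The change is worth making because it is nearly free and returns the expected cleaning-induced shift to zero, and with it the 5% level.

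**What to change.** In SAP 6.12.2:

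1. Before visual review, rename all EEG files with random codes and present them in random order, with the reviewer masked to visit. Unmask only after the cleaned data are frozen.
2. Report the number of removed segments by visit and by state, as a more precise form of the Item 3e commitment.
3. Repeat the paired t-test in SAP 4.4.2 on data with automatic rejection only, as a sensitivity analysis, to show whether the visual step drives the result.

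If masking is already practised, one sentence settles the first item. The section is written in the future tense, so the cost may be only a renaming step and one extra analysis run. If cleaning has been done unmasked, a masked repeat would take some days of the reviewer's time.

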### 6.12.3. EEG session-wise recording

During each session, beta band activity at baseline and during each trial were output from the neurofeedback device (in  $\mu\text{V}$ ) and manually noted for the neurofeedback and transfer condition. For each participant, the number of successful trials, defined as trials with a beta band activity below the baseline activity, with a possible range between 1-12 (for neurofeedback) and 1-6 (for transfer) trials, and condition-wise (i.e., for the neurofeedback and transfer condition) contrasts between regulation and baseline will be provided.

